### **Pregnancy and assessments of fertility**

All women of childbearing potential will have a urine or serum pregnancy test ( $\beta$ -HCG) during pre-study/baseline/EOS evaluations and during the course of the study only, if clinically indicated.

### **Additional blood samples**

Additional blood samples (unscheduled visits) can be scheduled for everolimus and tacrolimus trough levels determination at investigator's discretion.

## **7.7 Tolerability/acceptability**

Tolerability of study medication can be assessed from the rate of patients who withdraw prematurely from study medication or in whom study medication had to be converted to another immunosuppressive regimen due to abnormal laboratory results, adverse events, or toxicity.

All changes to the immunosuppressive medication dosing regimen will be recorded on the Dosage Administration Record CRF, along with the reason for change.

## **7.8 Resource utilization**

Not applicable

## **7.9 Health-related Quality of Life**

None

## **7.10 Pharmacovigilance**

Everolimus C0-h whole blood levels will be measured only in patients included into ARM I (=investigational arm), tacrolimus C0-h whole blood levels will be measured in all patients included into ARM I (=investigational arm) and Arm II (control arm).

- **Everolimus whole blood tests**

[figure not shown]
Analysis of the everolimus whole blood levels will be performed locally at the center during all visits throughout the study, starting on day 1 (Visit 2). Whole blood level for everolimus will be assessed as per local practice on blood taken within 5 minutes prior to everolimus administration (C-0h level).

- **Tacrolimus whole blood tests**

Analysis of the tacrolimus whole blood levels will be performed locally at the center during all visits throughout the study, starting on day 1 (Visit 2). Whole blood level for tacrolimus will be assessed by liquid chromatography coupled with mass spectrometry (LCMS). Values derived from enzyme based assays will be corrected (as described in the manufacturer's instructions).

## **7.11 Pharmacogenetics/pharmacogenomics**

None.

## 8 Safety monitoring

### 8.1 Serious adverse event reporting

To ensure patient safety, every SAE, regardless of suspected causality, occurring after the patient has provided informed consent and until 30 days after the patient has stopped study participation must be reported to Novartis within 24 hours of learning of its occurrence.

Any SAEs experienced after this 30 days period should only be reported to Novartis if the investigator suspects a causal relationship to the study drug.

Recurrent episodes, complications, or progression of the initial SAE must be reported as follow-up to the original episode, regardless of when the event occurs. This report must be submitted within 24 hours of the investigator receiving the follow-up information. An SAE that is considered completely unrelated to a previously reported one should be reported separately as a new event.

Information about all SAEs is collected and recorded on the Serious Adverse Event Report Form. The investigator must assess the relationship to study drug, complete the SAE Report Form in English, and send the completed, signed form by fax within 24 hours to the German Novartis Drug Safety & Epidemiology Department. The telephone and telefax number of the contact persons in the local department of Drug Safety & Epidemiology, are listed in the investigator folder provided to each site. The original copy of the SAE Report Form and the fax confirmation sheet must be kept with the case report form documentation at the study site.

Follow-up information is sent to the same person to whom the original SAE Report Form was sent, using a new SAE Report Form stating that this is a follow-up to the previously reported SAE and giving the date of the original report. The follow-up information should describe whether the event has resolved or continues, if and how it was treated and whether the patient continued or withdrew from study participation.

If the SAE is not previously documented in the Investigator's Brochure or Package Insert (new occurrence) and is thought to be related to the Novartis study drug, a Drug Safety & Epidemiology Department associate may urgently require further information from the investigator for Health Authority reporting. Novartis may need to issue an Investigator Notification (IN) to inform all investigators involved in any study with the same drug that this SAE has been reported.

### 8.2 Pregnancies

To ensure patient safety, each pregnancy in a patient on study drug must be reported to Novartis within 24 hours of learning of its occurrence. The pregnancy should be followed up to determine outcome, including spontaneous or voluntary termination, details of the birth, and the presence or absence of any birth defects, congenital abnormalities, or maternal and/or newborn complications.

Pregnancy should be recorded on a Clinical Trial Pregnancy Form and reported by the investigator to the German Novartis Drug Safety & Epidemiology Department. Pregnancy follow-up should be recorded on the same form and should include an assessment of the possible relationship to the Novartis study drug of any pregnancy outcome. Any SAE experienced during pregnancy must be reported on the SAE Report Form.

Pregnancy outcomes must be collected for the female partners of any males who took study drug in this study. Consent to report information regarding these pregnancy outcomes should be obtained from the mother.

### **8.3 Data Monitoring Board**

An external and independent Data Safety Monitoring Board (DSMB) will be instituted before study start. The DSMB will review safety-related issues in a meeting and will be entitled to make recommendations for changes in study conduct. Details on the function of the DSMB and the frequency of the DSMB meetings will be laid out in a separate DSMB Charter.

## **9 Data review and database management**

### **9.1 Site monitoring**

Before study initiation, at a site initiation visit or at an investigator's meeting, a Novartis representative will review the protocol and CRFs with the investigators and their staff. During the study, the field monitor will visit the site regularly to check the completeness of patient records, the accuracy of entries on the CRFs, the adherence to the protocol and to Good Clinical Practice, the progress of enrollment, and to ensure that study drug is being stored, dispensed, and accounted for according to specifications. Key study personnel must be available to assist the field monitor during these visits.

The investigator must maintain source documents for each patient in the study, consisting of case and visit notes (hospital or clinic medical records) containing demographic and medical information, laboratory data, electrocardiograms, and the results of any other tests or assessments. All information on CRFs must be traceable to these source documents in the patient's file. Data not requiring a separate written record will be defined before study start and will be recorded directly on the CRFs, which will be documented as being the source data. The investigator must also keep the original informed consent form signed by the patient (a signed copy or a second original is given to the patient).

The investigator must give the monitor access to all relevant source documents to confirm their consistency with the CRF entries. Novartis monitoring standards require full verification for the presence of informed consent, adherence to the inclusion/exclusion criteria, documentation of SAEs, and the recording of data that will be used for all primary and safety variables. Additional checks of the consistency of the source data with the CRFs are performed according to the study-specific monitoring plan. No information in source documents about the identity of the patients will be disclosed.

### **9.2 Data collection**

Designated investigator staff must enter the information required by the protocol onto the Novartis CRFs that are printed on 3-part, non-carbon-required paper. Field monitors will review the CRFs for completeness and accuracy and instruct site personnel to make any

required corrections or additions. The CRFs are forwarded to Data Management by field monitors, one copy being retained at the investigational site. Once the CRFs are received by Data Management, their receipt is recorded and they are reviewed prior to data entry.

### **9.3 Database management and quality control**

Data from the CRFs are entered into the study database by Contract Research Organization staff following their own internal standard operating procedures that have been reviewed and approved by Novartis. Subsequently, the entered data are systematically checked by Data Management staff, using error messages printed from validation programs and database listings. Obvious errors are corrected by Data Management personnel. Other errors or omissions are entered on Data Query Forms, which are returned to the investigational site for resolution. The signed original and resolved Data Query Forms are kept with the CRFs at the investigator site, and a copy is sent to Novartis so the resolutions can be entered into the database. Quality control audits of all key safety and efficacy data in the database are made prior to locking the database.

Concomitant medications entered into the database will be coded using the WHO Drug Reference List, which employs the Anatomical Therapeutic Chemical classification system. Medical history/current medical conditions and adverse events will be coded using the Medical dictionary for regulatory activities (MedDRA) terminology.

At the conclusion of the study the occurrence of any protocol violations will be determined. After these actions have been completed and the database has been declared to be complete and accurate, it will be locked and the treatment codes will be unblinded and made available for data analysis. Any changes to the database after that time can only be made by joint written agreement between the Trial Statistician and Statistical Reporting and the Clinical Trial Leader.

## **10 Data analysis**

The data will be analyzed by Novartis and/or by the designated CRO. Any data analysis carried out independently by the investigator(s) should be submitted to Novartis before publication or presentation. The final analysis will be done when all patients have completed their Visit 9 (Month 12) assessment or discontinued prematurely. It is planned that the data from all centers that participate in this protocol will be used, so that an adequate number of patients will be available for analysis.

Data will be summarized with respect to demographic and baseline characteristics, efficacy observations and measurements, safety observations and measurements, and pharmacokinetic measurements. All summary statistics will be presented by treatment group. Categorical variables will be summarized by absolute and relative frequencies. Continuous variables will be summarized by descriptive statistics of the number of valid and missing observations, mean, standard deviation, minimum, median and maximum. Time-to-event data including rates of affected patients will be assessed by Kaplan-Meier statistics. Group comparisons will be performed using appropriate two-sided statistical tests.

### **10.1 Populations for analysis**

The **Full Analysis Set (FAS)** will consist of all patients as randomized that received at least one dose of study drug and have a valid baseline assessment of the primary efficacy variable.

Following the intent-to-treat principle, patients will be analyzed according to the treatment they were assigned to at randomization.

The **Per-protocol Set (PP)** will consist of a subset of patients of the FAS who did not show major deviations from the protocol procedures that may have an impact on the study outcome. Reasons for exclusion of the Per-protocol Set may be (but are not limited to): deviations from entry criteria, errors in treatment assignment, use of excluded/forbidden/un-allowed medication, premature discontinuation of randomized treatment or study, poor compliance, loss to follow-up, missing data in the primary efficacy variable. Criteria that are assumed to have such an impact will be defined in the Protocol Deviations Module of the Validation and Planning (VAP) documentation, and assessed before database lock during the data review meeting.

The **Safety Set** will consist of all patients that received at least one dose of study drug and had at least one post-baseline safety assessment. Patients will be analyzed according to treatment received. Of note, the statement that a patient had no adverse events also constitutes a safety assessment.

## **10.2 Patient demographics/other baseline characteristics**

Demographic and other baseline characteristics will be summarized for the full analysis set (FAS) by treatment group. Baseline characteristics include prior medication, past/current medical conditions and transplant history.

Medical history will be coded using MedDRA and will be presented by MedDRA system organ class, preferred term and treatment group. Separate tables will be provided for past medical conditions and current medical conditions. Prior medication will be coded according to the WHO Drug Reference List and summarized by ATC class, preferred term and treatment group.

## **10.3 Treatments (study drug, rescue medication, other concomitant therapies, compliance)**

### **10.3.1 Study medication**

Duration (days) of drug exposure to each individual component of the immunosuppressive treatment regimen will be summarized using descriptive statistics. Duration of drug exposure will be calculated as the difference between the last and first day of drug application +1. Dosage averages will be calculated including and excluding zero doses for periods of temporary interruption of treatment regardless of whether this was due to safety reasons or patients' non-compliance. Daily dose levels will be summarized descriptively. Frequencies of the number of patients with any dose reduction (including temporary dose interruption) as well as the number of dose reductions by reason will be given. These analyses will be performed by treatment group for the safety set.

Frequency tables displaying cumulative frequencies of 'crude rates' will be presented for the number of patients with trough levels below/within/above the defined therapeutic windows drug and by visit. If appropriate, treatment groups will be compared exploratory using the Pearson's Chi-Square test (where all expected numbers are at least 1), otherwise Fisher's exact test will be used ([Campbell 2007](#)). Furthermore, frequency tables for the number of

patients with trough levels below/within/above the defined therapeutic windows drug and by period.

### **10.3.2 Concomitant therapy**

Prior and concomitant medications and non-drug therapies will be coded according to WHO-DRL. Concomitant medications taken through the study will be summarized by preferred term, ATC class and treatment group for the safety set. Dosages of corticosteroids will be converted to prednisolone dose equivalents and summarized as described above.

## **10.4 Analysis of the primary objective(s)**

The primary objective of the trial is to demonstrate that an immunosuppressive regimen based on everolimus (EVR) in co-exposure with tacrolimus (TAC) has superior efficacy compared to tacrolimus alone on estimated glomerular filtration rate (MDRD-4 formula) at 12 months after transplantation in *de novo* liver transplant recipients.

### **10.4.1 Variable**

The primary efficacy variable of this trial is the renal function at Month 12 after baseline assessed by estimated GFR based on recalculated values according to the MDRD-4 formula:  $eGFR [mL/min/1.73m^2] = eGFR = 186.3 * C^{1.154} * A^{-0.203} * G * R$ , where C is the serum concentration of creatinine [mg/dL], A is age (years), G=0.742 when gender is female, otherwise G=1, R=1.21 when race is black, otherwise R=1.

### **10.4.2 Statistical hypothesis, model, and method of analysis**

The trial tests the null hypothesis that the treatment difference (investigational minus control) in mean eGFR at Month 12 after baseline is zero versus the alternative hypothesis that the treatment difference is different from zero.

The hypotheses will be tested with an analysis of covariance (ANCOVA) with treatment , center, HCV-Class (positive, negative) and MELD ( $\leq 30$  vs  $> 30$ ) as factors, and eGFR at Visit 1 (Baseline) as covariate. Raw as well as adjusted means (= LS-means, LS: least square means) will be presented for the treatment contrast together with a two-sided *p* value and the appropriate confidence interval, respectively. The significance level will be 5% (two-sided). There are no multiplicity issues to be addressed since only the hypothesis of superior efficacy of the investigational vs. the control regimen will be tested confirmatory.

The Full Analysis Set will be used for the primary analysis. If patients of the FAS are switched from the reference to the investigational group during the study, they will be analyzed in their randomized group. If appropriate, a subgroup analysis will be performed comparing patients of the reference group with and without switch to the investigational group including a further analysis comparing the subgroups to the randomized investigational group. If treatment will be modified in the investigational group, they will be analyzed as randomized.

### **10.4.3 Handling of missing values/censoring/discontinuations**

Missing values in cGFR will be imputed with the last valid observed value from that patient (LOCF). Under the assumption that the eGFR will remain fairly stable in the control group but will probably improve in the investigational group, this strategy corresponds to a

conservative estimate of the treatment effect. Alternative missing value procedures may be performed additionally as sensitivity analyses (see below).dealt with by multiple imputation ([Molenberghs & Kenward 2007](#); [White, Royston & Wood 2010](#)). The multiple imputation procedure will be presented in detail (e.g. seed value, method for imputation) in the statistical analysis plan to be finalized before database lock.

#### 10.4.4 Supportive analyses

For sensitivity, the following analyses will be performed:

The primary analysis will be repeated with the Per-protocol Set using the same ANCOVA model as described above.

As a further supportive analysis, a Mixed Model for Repeated Measures (MMRM) will be fitted using treatment group, visit (as a categorical time variable) and subject as categorical variables ([Molenberghs & Kenward 2007](#)). Assuming that the time profile is not the same in the two treatment groups, a full visit-by-treatment interaction will be used. If a baseline is to be included in the model, the baseline-by-time interaction will be included in the model, otherwise strange and unrealistic restrictions on the implied covariance structure would be made in this case. An unstructured covariance matrix will be used. Since there are sufficient data, using a different covariance matrix in each treatment group might be considered:

```
proc mixed;
class subject visit treatment;
model gfr = baseline treatment visit baseline*visit treatment*visit / s ddfm=kr;
repeated time / subject = subject type = un group=treatment;
run;
```

The estimated adjusted treatment effect as well as the treatment contrast will be presented for the Month 12 visit together with appropriate two-sided 95% confidence intervals. The model will be fitted for both, the FAS as well as the PP set.

Only in case of substantial drop-out (>20%) or if relevant differences in the drop-out-patterns between the two treatment groups are observed, a multiple imputation of missing values ([Molenberghs & Kenward 2007](#); [White, Royston & Wood 2010](#)) will be performed as an alternative to account for missing values. The necessity of this procedure will be decided during the data review meeting, computational details (e.g. seed value, method for imputation) will be described in the statistical analysis plan to be finalized before database lock.

The course of eGFR will be summarized descriptively by visit and treatment group for the FAS. Only observed cases will be used (no data imputed by multiple imputation, since multiple imputation implies the creation of more than one imputed value per patient). Absolute and percent changes from baseline to each post-baseline measure will be calculated by treatment group for each study visit as post-baseline minus baseline value. Between-group as well as within-group comparisons will be performed exploratory using suitable parametric (*t*-test/paired *t*-test) and nonparametric (Wilcoxon rank-sum test/Wilcoxon signed-rank test) statistical tests for paired and two-sample data, respectively.

## 10.5 Analysis of secondary objectives

### 10.5.1 Efficacy (secondary)

The following secondary efficacy variables will be analyzed in an explorative manner for the full analysis set (FAS):

- efficacy-related endpoints, such as acute rejection, treated biopsy proven acute rejection (BPAR), graft loss, death and loss to follow-up (as composites or individual endpoints)
- endpoints related to renal function: eGFR using various methods (MDRD-4, Nankivell, Cockcroft-Gault, CKD EPI and Hoek formulae

#### Efficacy-related objectives

The incidence of efficacy-related endpoints will be estimated using the Kaplan-Meier method. The number of events as well as the number of censored observations will be presented. Kaplan-Meier estimates will be presented by visit up to Month 12. Percentiles (25%, median, 75%) of the event time distribution will be presented together with their two-sided 95% confidence interval. The two groups will be compared using the log-rank test. Kaplan-Meier curves will be displayed graphically. For rejections, Kaplan-Meier analyses may be stratified by severity grade.

The following endpoints will be analyzed:

- Incidence of a composite of treated biopsy proven acute rejection (BPAR), graft loss or death at Month 12.
- Incidence of a composite of treated BPAR, graft loss, death or loss to follow-up.
- Incidence of a composite of death or graft loss.
- Incidence of acute rejection, treated acute rejection, BPAR, treated BPAR, graft loss, or death

#### Renal function-related objectives

Renal function as assessed by cGFR calculated according to the CKD-EPI, Cockcroft-Gault, Nankivell, MDRD-4, and Hoek formulas (see [Section 7.5](#)) will be analyzed using the ANCOVA model specified for the primary analysis. Raw as well as adjusted means will be presented for the treatment contrast together with its confidence interval and two-sided exploratory  $p$  values separately for each time point. Missing values will be dealt with in the ANCOVA analysis by multiple imputation. Additionally to the analysis at Month 12, an analysis at Month 6 will be performed.

Descriptive statistics for observed values and changes from baseline as well as within-group and between-group comparisons using suitable parametric and non-parametric statistical tests will be displayed by visit and treatment group. Additionally, descriptive statistics will be presented for the following subgroups:

- age: <60 vs.  $\geq$ 60 years
- gender: male vs. female
- renal function at baseline: 30 – <45, 45 – <60,  $\geq$ 60 mL/min/1.73m^2; <45 vs  $\geq$ 45 mL/min/1.73m^2, <60 vs.  $\geq$ 60 mL/min/1.73m^2
- HCV status at baseline: positive vs. negative

- lab MELD score at baseline:  $\leq 14$ ,  $15 - 19$ ,  $20 - 24$ ,  $25 - 29$ ,  $\geq 30$

Serum creatinine as well as the urinary protein/creatinine ratio will be summarized using descriptive statistics for observed values and changes from baseline. Within-group and between-group comparisons will be performed using suitable parametric and non-parametric statistical tests and will be displayed by visit and treatment group.

The incidence of patients experiencing a decline in eGFR of  $<10$ ,  $10 - <15$ ,  $15 - <20$ ,  $20 - <25$ , and  $\geq 25$  mL/min/1.73m^2 from baseline will be analyzed using frequency tables by visit and treatment group. Treatment groups will be compared exploratory using the Pearson's Chi-Square test (where all expected numbers are at least 1), otherwise Fisher's exact test will be used.

The incidence of proteinuria of  $0.5 - <1.0$  g/day,  $1.0 - <3.0$  g/day and  $\geq 3.0$  g/day will be analyzed using frequency tables by visit and treatment group. Treatment groups will be compared exploratory using the Pearson's Chi-Square test (where all expected numbers are at least 1), otherwise Fisher's exact test will be used.

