## **10.7 Sample size calculation**

The trial tests the null hypothesis that there is no difference in renal function, estimated by cGFR according to the MDRD-4 formula, at 12 months after randomization between the everolimus-based tacrolimus-minimization regimen and the tacrolimus-based control regimen versus the alternative hypothesis that the difference is 7.0 ml/min/1.73m^2. A sample size of 105 in each group will have 80% power to detect a difference in means of 7.0 ml/min/1.73m^2 assuming that the common standard deviation is 18.0 ml/min/1.73m^2 with a 5% two-sided significance level. (One will decide in favor of H1 when the difference in means would be 5.1 ml/min/1.73m^2 or greater in favor of the everolimus-based group.) To adjust the sample size for a common drop-out rate (DOR) of 20% (using the formula  $N_{adj}=N/(1-DOR)^2$ ), 165 patients need to be randomized per group. Sample sizes were estimated using NQuery (Version 6.1) procedure “Two-group *t*-test for equal means (equal n’s)”.

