## 1.3 Study objectives and endpoints

The primary objective was to demonstrate that an immunosuppressive regimen based on everolimus (EVR) in co-exposure with tacrolimus (TAC) has superior efficacy compared to tacrolimus alone on estimated glomerular filtration rate (MDRD-4 formula) at Month 12 in de novo liver transplant recipients.

The key secondary objective was to evaluate the incidence of a composite of treated biopsy proven acute rejection (BPAR), graft loss or death until Month 12.

Other efficacy related secondary objectives were

- To evaluate the incidence of a composite of treated BPAR, graft loss, death or loss to follow-up at months 6 and 12.
- To evaluate the incidence of each component of the composite efficacy endpoint at month at months 6 and 12.
- To evaluate the incidence of a composite of death or graft loss at months 6 and 12.
- To evaluate treated BPAR by: (1) incidence, (2) time to event, (3) severity, (4) final clinical diagnosis and outcome.
- To evaluate any acute rejection by: (1) incidence, (2) time to event, (3) severity(4) final clinical outcome outcome.
- To evaluate the incidence of:
  - Treated acute rejection.
  - BPAR.

- Treated BPAR

Other renal function related related secondary objectives were

- To evaluate the evolution of post-randomization renal function over time assessed by the change in estimated GFR (MDRD-4), including to Months 6, and 12.
- To evaluate renal function by eGFR using various methods (MDRD-4, Nankivell, Cockcroft-Gault, CKD-EPI and Hoek formulae).
- To evaluate the incidence of patients experiencing a decline in eGFR (MDRD-4) of < 10, 10<15, 15<20, 20<25, and  $\geq$  25 mL/min/1.73m^2 from Screening, Week 2 post transplantation (Day 15) and randomization to Months 6, and 12.
- To evaluate serum creatinine at various time points.
- To evaluate renal function and change in eGFR from screening, randomization, and Week 2 post transplantation (Day 15) to Months 6 and 12 eGFR in following subgroups: age (< 60 and  $\geq$  60 years), gender, race, renal function strata (< 30, 30<45, 45<60,  $\geq$  60 mL/min/1.73m^2, below/above 45 mL/min/1.73m^2, below/above 60 mL/min/1.73m^2), HCV status, lab MELD score categories ( $\leq$ 14, 15-19, 20-24, 25-29,  $\geq$  30), and diagnosis leading to transplantation.
- To evaluate urinary protein/creatinine ratio at various time points.
- To evaluate the incidence of proteinuria. as adverse event of special interest.

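### The five ordered eGFR-decline categories are compared by a test that ignores their order; naming an ordinal test would gain power at no cost

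*Protocol*

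**What the plan says.** Protocol 10.5.1, under the renal function objectives, states: "The incidence of patients experiencing a decline in eGFR of" <10, 10–<15, 15–<20, 20–<25 and ≥25 mL/min/1.73m² "from baseline will be analyzed using frequency tables by visit and treatment group. Treatment groups will be compared exploratory using the Pearson's Chi-Square test". This holds if every expected count is at least 1; otherwise Fisher's exact test is used. No trend, rank or proportional-odds test is named for this table.

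SAP 1.3 keeps the objective: "To evaluate the incidence of patients experiencing a decline in eGFR (MDRD-4) of" the same five bands. SAP 2.5.1 and 2.5.2 give methods for the other eGFR formulas and for proteinuria, and do not mention the decline bands. The list of changed statistical methods in SAP Section 4 does not mention them either.

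The protocol labels the secondary efficacy analyses as explorative. Protocol 10.8 and SAP Section 3 say that power for secondary variables was not investigated.

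**The concern.** The bands run from least to most decline. If everolimus with reduced tacrolimus preserves eGFR, as the trial hypothesises, patients should move in one direction along them. Pearson's chi-square and Fisher's exact test treat the bands as unlabelled boxes. On a 2×5 table they look for any departure from equal proportions, including patterns with no direction, such as more patients in one middle band and fewer in the next. The p-value alone does not show that one arm declines less. The reader has to take that from the table.

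What is at stake is modest. A non-significant p-value could stand beside a significant analysis of continuous eGFR only because the table's test is the weaker one. Exploratory p-values are still reported and read.

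**Working it through.** **Inputs from the documents (Protocol 10.7).** "A sample size of 105 in each group will have 80% power to detect a difference in means of 7.0" mL/min/1.73m², "assuming that the common standard deviation is 18.0", "with a 5% two-sided significance level"; 20% drop-out; 165 randomized per group.

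**The plan's own figure.** A two-sample t-test with difference 7.0, SD 18.0 and n = 105 per group has power 80.1%. The inflation is 105/(1 − 0.20)² = 164.06, rounded up to 165. Both figures reproduce.

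**Assumptions not in the documents.** Change is normal, with a pure shift of 7.0 between arms. SD of change = 18 × √(2(1 − r)), where r is the baseline-to-Month-12 correlation: 21.3, 18.0 and 13.9 for r = 0.3, 0.5 and 0.7. Control mean decline is 0, 5 or 10. The comparison is one 2×5 table.

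**Central case: r = 0.5, control mean decline 0.** Cutting the two normal curves at 10, 15, 20 and 25 gives

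| Band | <10 | 10–<15 | 15–<20 | 20–<25 | ≥25 |
|---|---|---|---|---|---|
| Control p | 0.711 | 0.087 | 0.069 | 0.051 | 0.082 |
| EVR/TAC q | 0.828 | 0.062 | 0.044 | 0.029 | 0.038 |

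The smallest expected count at 105 per group is 105 × (0.051 + 0.029)/2 = 4.2, so Pearson applies and the Fisher fallback does not.

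*Pearson.* Noncentrality = n × Σ(p − q)²/(p + q) = 105 × (0.0089 + 0.0043 + 0.0056 + 0.0059 + 0.0166) = 105 × 0.0413 = 4.33 on 4 df, critical value 9.49.

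*Wilcoxon-score test.* With pooled proportions m = (p + q)/2 and midranks (ridits) s = 0.385, 0.806, 0.872, 0.920, 0.970, noncentrality = n × [Σ(p − q)s]² / [2Σm(s − 0.5)²] = 105 × 0.0607² / (2 × 0.0453) = 4.26 on 1 df, critical value 3.84.

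The signal is almost the same (4.33 and 4.26). Pearson sets it against 4 df and the ordinal test against 1. The large-sample powers are 35% and 54%. Simulation gives 33% and 55%. The t-test on uncut change has 80%.

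**Range.** Simulated power, Pearson / Wilcoxon-score (loss in points, taken before rounding):

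| Control mean decline | r | 105 per group | 165 per group |
|---|---|---|---|
| 0 | 0.3 | 26 / 44 (18) | 41 / 63 (22) |
| 0 | 0.5 | 33 / 55 (21) | 52 / 74 (22) |
| 0 | 0.7 | 44 / 69 (25) | 69 / 87 (19) |
| 5 | 0.3 | 30 / 49 (19) | 46 / 68 (22) |
| 5 | 0.5 | 40 / 61 (22) | 61 / 81 (20) |
| 5 | 0.7 | 59 / 80 (21) | 82 / 94 (12) |
| 10 | 0.3 | 33 / 53 (20) | 50 / 72 (21) |
| 10 | 0.5 | 45 / 67 (22) | 67 / 85 (18) |
| 10 | 0.7 | 68 / 86 (18) | 89 / 97 (8) |

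Repeat runs differ by up to about one point; shorter runs give 53 / 75 for the stable-control case at 165. After 20% drop-out (165 × 0.8 = 132 per group) that case gives 42 / 64. Over a wider grid (SD of change 14 to 25.5, control mean decline −5 to 15) the loss is 6–28 points, smallest where both tests are near their ceiling.

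**Type I error** with no difference, 105 per group: Pearson 4.8%, Wilcoxon-score 5.2%. The gain does not come from an inflated error rate.

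**The case against.** **Renal decline is tested elsewhere, and better.** A reader might infer that the chi-square is the plan's only between-arm test of how far eGFR falls. It is not. Protocol 10.4.4 compares absolute and percent change from baseline at each visit by t-test and Wilcoxon rank-sum test, and SAP 2.3.6 keeps the t-test. ANCOVA at Months 6 and 12 and the MMRM also compare the arms on continuous eGFR. This stands, and it limits the consequence.

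**The test would not usually miss the planned effect.** At 105 per group Pearson's power is below one half in seven of the nine scenarios. At the randomized 165 it is about one half or more in seven of nine. The ordinal test itself would miss about 45% of the time in the central case at 105. The statement that the effect would usually be missed cannot be made in general.

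**The 2×5 reading is inferred.** The protocol never says one global test. The expected-count rule carries a citation in Protocol 10.3.1 to a paper on two-by-two tables, which makes separate tests per band plausible. Against that, the same section applies the rule to a three-level variable. If the only comparison were <10 against ≥10, power in the central case would be about 52–53% at 105 and 72% at 165, only 2–3 points below the ordinal test. Separate tests for all five bands would still ignore order and would add multiplicity.

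**The SAP may have dropped the test.** SAP Section 4 is not a complete record. The chi-square for trough levels (Protocol 10.3.1, SAP 2.3.1) and the Wilcoxon test on eGFR change (Protocol 10.4.4, SAP 2.3.6) disappear without being listed. So one cannot say that the SAP retains Pearson here. Only the protocol specifies a test, and the SAP leaves the choice open.

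**Pearson is valid, and the analysis is exploratory.** Both are true. The frequency table beside the test also shows the direction. What remains is that the one test named for these bands is a weaker choice than another that uses the same data.

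**Conclusion.** The point holds as a free improvement. The protocol names an unordered test for an ordered outcome, and the SAP does not supply a better one. On the 2×5 reading, with a normal shift of 7.0, an SD of change near 18 and a control mean decline of 0 to 10, the loss against a Wilcoxon-score test is about 21–22 points at 105 per group and about 18–22 points at 165. Over correlations of 0.3 to 0.7 it is about 8–25 points. These figures depend on an SD of change and category proportions that the documents do not give, and on a consistent one-way shift. They should not be quoted as a fixed property of the plan. The simulated ordinal test was unstratified. No primary or key secondary conclusion depends on this comparison.

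**What to change.** In Protocol 10.5.1, replace Pearson/Fisher for the eGFR-decline bands with a Cochran-Mantel-Haenszel row-mean-score test using modified ridit scores, stratified by the randomization factors HCV status and lab MELD (≤30, >30). Add the same sentence to SAP 2.5.2, which has no text on these bands. Keep the frequency table by visit and arm. State that the table describes the continuous eGFR comparison, which carries the inference.

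The cost is one sentence in each document and a different option in the frequency procedure. No new data are needed. Because the analysis is exploratory, no significance level is affected.
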